### 4. STUDY POPULATION

# 4.1 Population (base)

The research population will be drawn from the patients that visit the ACTA. These patients are particularly from Amsterdam and surrounding areas. The study subjects with periodontitis that will be enrolled in this study are referred to the periodontal clinic of ACTA for diagnosis and treatment of periodontitis. The control subjects without periodontitis will be selected among subjects that visit the dental school of ACTA for regular dental checkups.

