### 8.3 Study procedures

All subjects with periodontitis, diagnosed in a periodontology clinic, will be asked to participate. Subjects without periodontitis, visiting the dental school for a dental check-up, are selected and also asked to participate. The selection of subjects without periodontitis will be based on the following criteria: no interproximal alveolar bone loss on  $\leq$ 1-year-old dental bitewing radiographs, no fulfillment of criteria for the classification of periodontitis according to the Centers for Disease Control and Prevention – American Academy of Periodontology (CDC-AAP) case definition (Appendix 5) (23).

Medical information, a periodontal chart (for periodontitis patients) or a periodontal screening index (for subjects without periodontitis) and a standard dental radiographic chart will be retrieved from the patient records. During the dental appointment blood will be obtained by a finger stick. Blood analysis will be performed to acquire data on the condition of the patients.

A questionnaire about demographic characteristics will be filled in together with the periodontist or researcher, including the measurement of the systolic and diastolic blood pressure, body length and weight, waist and neck circumference. A questionnaire for assessment of the OSAS risk and a questionnaire about physical activity (IPAQ) will be asked to be filled in by the participant.

At the dental appointment, all subjects (with or without periodontitis) will undergo the following assessments during the periodontal intake or regular dental check-up:

- 1. General, medical and dental anamnesis (standard procedure)
- 2. Clinical periodontal evaluation to define the presence and severity of periodontitis (standard procedure)
- 3. Dental x-rays, when indicated for periodontitis or other dental pathology (standard procedure)
- 4. Measurement of systolic and diastolic blood pressure (standard procedure)
- 5. Measurement of length and body weight, waist and neck circumference, a questionnaire for demographic characteristics, an International Physical Activity Questionnaire (IPAQ) and an OSAS risk questionnaire. (extra procedure)

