### **10.1 Primary study parameter(s)**

The cases and controls are a priori defined by inclusion and exclusion criteria. The STROBE guideline will be followed and a flow diagram will be generated of how many individuals have been screened, invited to participate, included and analysed (29). All initially included study subjects will form part of the data analysis (intention to treat). Type I error will be controlled by including a sufficient number of cases and controls to avoid multiplicities and to apply Bonferroni corrections where applicable. Secondly, we have determined the minimal sample size on the basis of an appropriate power calculation (see chapter 4.4).

The prevalence of (pre)diabetes, the 10-year risk of ASCVD, the prevalence of MetS and the prevalences of OSAS risks (categorical variables) within the study population will be compared with parametric and non-parametric tests (ANOVA and  $Chi^2$ -test). Where applicable, analyses will be corrected for multiple testing (Bonferroni). The significance level will be set to p<0.05.

The prevalence of (pre)DM among cases and controls will be firstly reported without adjustment of any of potential covariates. In a second exploratory analysis we will adjust the prevalence for general and diabetes and ASCVD related characteristics of the study population: sex, age, ethnicity (origin of parents), education level, smoking habits, relatives with DM, history of periodontal treatment, diagnosis of hypertension, diagnosis of hypercholesterolemia, diagnosis of DM and the BMI, amount of physical activity.

The 10-year risk of ASCVD will be calculated according to the algorithm from the ESC guidelines, which is adapted to the Dutch situation. No further adjustments will be done.

The prevalence MetS will be calculated according to the criteria of the NCEP ATP III guidelines. No covariates will be included.

The risk for OSAS will be assessed by the OSAS questionnaire. No further adjustments will be done. However, the results will be explored in relation to having periodontitis, the

background characteristics, the blood chemistry outcomes and having (pre)diabetes and the 10-year risk for ASCVD.

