### 10.2 Secondary study parameter(s)

The secondary research aim is to investigate whether there are differences between severe periodontitis and mild/moderate periodontitis. As such, mild/moderate periodontitis will be labelled as "control" while severe periodontitis patients are labelled as "cases". In secondary analyses exact procedures are followed as described above for the primary outcomes.

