### **10.3 Other study parameters**

Other study parameters that will be obtained and used as covariates are sex (M/F), age (years), ethnicity (origin of parents) (Europe/Non-Europe), education level (high/low), smoking habits (yes/no), diagnosis of hypertension (yes/no), diagnosis of ASCVD (yes/no), medical treatment for ASCVD (yes/no), relatives with ASCVD (yes/no), diagnosis of hypercholesterolemia (yes/no), medical treatment for hypercholesterolemia (yes/no), diagnosis of DM (yes/no), relatives with DM (yes/no), history of periodontal treatment (yes/no), height (cm) and body weight (kg) (for determining the BMI), neck and waist circumference (cm), blood pressure (mmHg), physical activity (Metabolic Equivalent of Task).

**10.4 Interim analysis (if applicable)** NA

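### Adjusting the exploratory (pre)DM comparison for history of periodontal treatment conditions on a near-marker of being a periodontitis case, which costs precision and can distort the odds ratio in either direction

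*Combined protocol and SAP*

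**What the plan says.** Under section 10.1 the prevalence of (pre)DM in cases and controls "will be firstly reported without adjustment of any of potential covariates". The section then continues: "In a second exploratory analysis we will adjust the prevalence for general and diabetes and ASCVD related characteristics of the study population". The list that follows contains "relatives with DM, history of periodontal treatment, diagnosis of hypertension, diagnosis of hypercholesterolemia, diagnosis of DM and the BMI". Section 10.3 codes the item as "history of periodontal treatment (yes/no" and gives no definition, time window or reason for including it. No covariate adjustment is planned in 10.1 for ASCVD risk, MetS or OSAS risk.

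The groups are formed by periodontal status. Section 8.3 requires of controls "no interproximal alveolar bone loss on" bitewings no more than a year old, and "no fulfillment of criteria for the classification of periodontitis according to the Centers for Disease Control and Prevention" (with the Academy of Periodontology, Appendix 5). Section 4.1 says that the periodontitis subjects "are referred to the periodontal clinic of ACTA for diagnosis and treatment of periodontitis". For severe versus mild/moderate disease, section 10.2 states: "In secondary analyses exact procedures are followed as described above for the primary outcomes".

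**The concern.** A covariate belongs in this model if it could confound the link between periodontitis and (pre)DM, as age, smoking or ethnicity could. Periodontal treatment is of another kind: people receive it because they have periodontitis, which is the grouping variable. It does not fit the plan's own description of the list as general, diabetes-related and ASCVD-related characteristics.

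The control criteria make matters worse. Treated periodontitis would usually leave bone or attachment loss, so a subject who passes section 8.3 will seldom have been treated for it. The treatment coefficient is then estimated almost wholly among cases, and the group coefficient mainly compares never-treated periodontitis with controls. The objective in section 2 is periodontitis versus no periodontitis.

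At stake is the only planned (pre)DM analysis that deals with confounding. Cases and controls come from different patient streams (4.1), there are no exclusion criteria (4.3), and no matching is described. Readers will look to the adjusted result to see whether the crude difference survives.

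**Working it through.** **1. The plan's own figure.** Section 4.4 gives 261 per group for DM prevalences of 8.5% and 18.1%, alpha 0.05 (two-sided assumed) and 90% power. With the pooled-variance formula and mean prevalence 0.133:

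n = [1.960 × √(2 × 0.133 × 0.867) + 1.282 × √(0.181 × 0.819 + 0.085 × 0.915)]² / 0.096² = 260.9, or 261.

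The figure reproduces and involves no covariate.

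**2. Inputs for the adjusted comparison.** Pilot new-DM rates from section 1 (Hypothesis): controls 8.5%, mild/moderate 9.9%, severe 18.1%. With 261 per group, all cases together have (9.9% + 18.1%)/2 = 14.0%. The documents give no preDM rates, so DM stands in for (pre)DM. They also give no treated share for any group and no association between treatment and DM. Those values are assumptions below.

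Unadjusted odds ratio: (0.140/0.860) / (0.085/0.915) = 0.1628/0.0929 = 1.75.

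**3. Overlap.** With 50% of cases and 2% of controls treated (assumed), there are 0.50 × 522 = 261 treated cases and 0.02 × 261 ≈ 5 treated controls.

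**4. Effect on the odds ratio.** Let q be the treated share in a group, g the odds ratio between treatment and DM within group, and p the group's DM prevalence. The untreated risk u solves

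(1 − q)·u + q·[g·u/(1 − u)] / [1 + g·u/(1 − u)] = p.

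The adjusted odds ratio is the odds of u in cases divided by the odds of u in controls. For q = 50% in cases and 2% in controls:

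| g (assumed) | u, cases | u, controls | Adjusted OR |
|---|---|---|---|
| 0.67 | 16.4% | 8.55% | 0.1960/0.0935 = 2.10 |
| 1.0 | 14.0% | 8.50% | 0.1628/0.0929 = 1.75 |
| 1.5 | 11.6% | 8.43% | 0.1310/0.0920 = 1.42 |
| 2.0 | 9.9% | 8.36% | 0.1103/0.0912 = 1.21 |

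With only 10% of cases treated (2% of controls), the same four values of g give 1.80, 1.75, 1.69 and 1.64. With 90% treated they give 2.48, 1.75, 1.22 and 0.94.

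**5. Effect on precision.** VIF = 1/(1 − φ²), where φ is the correlation between group (522/261) and treatment history:

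- 30% of cases and 5% of controls treated: φ² = 0.082, VIF 1.09.
- 50% and 2%: φ² = 0.228, VIF 1.30.
- 70% and 0%: φ² = 0.4375, VIF 1.78.

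This is a linear-model approximation. A logistic fit to the expected cell counts at 50% and 2% raises the standard error by a factor of 1.08 to 1.16 over the four values of g. At g = 1 the factor is 1.10: precision is lost with no change in the estimate.

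**6. The secondary comparison (10.2).** Severe versus mild/moderate has an unadjusted odds ratio of (0.181/0.819) / (0.099/0.901) = 2.01. If 50% of severe and 30% of mild/moderate cases were treated (assumed), adjustment gives 2.18 (g = 0.67), 2.01 (1.0), 1.86 (1.5) and 1.76 (2.0). The standard error rises by a factor of only about 1.02, so there is no shortage of overlap here.

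**The case against.** A reader might infer that adjustment necessarily removes part of the effect and pulls the estimate towards no association. The documents do not support that. It needs treatment history to go with more DM within group, for instance by marking longer or more severe disease, and nothing in the documents establishes this. With no such link only precision is lost. With an inverse link, for example if treated patients have better contact with care, the odds ratio rises. The study is also cross-sectional and presents periodontitis as a possible sign of metabolic disease, so the target is an association rather than an effect that could be partly removed.

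A reader might also infer that the main (pre)DM result or the study size is compromised. Neither is. The unadjusted comparison comes first, the adjusted one is labelled exploratory, and a difference in prevalence found by screening in a dental setting is answered directly by the crude figures. This limits the weight of the point. It does not make the covariate suitable for the one model meant to handle confounding.

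The objection has most force for section 10.2. Both severity groups can contain treated patients, so the near-empty cell is absent. Earlier treatment can also change the probing depths that partly define current severity (Appendix 5), so it may precede the measured category instead of only following from it. Deleting it there cannot be justified by the argument used for 10.1.

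Two further points stand. The rarity of treated controls is inferred, and an undefined yes/no item could pick up cleaning for gingivitis. The same covariate list also contains diagnosis of DM, which lies close to the outcome itself and is the more serious over-adjustment. That is a separate matter, but removing treatment history alone will not make the adjusted model easy to interpret.

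**Conclusion.** The point holds for the exploratory adjusted (pre)DM comparison of periodontitis versus controls. There, treatment history is a consequence and near-marker of group membership, and the plan offers no reason to treat it as a confounder. Including it changes which contrast is estimated and loses precision (VIF about 1.09 to 1.78 if 30-70% of cases and 0-5% of controls are treated). At 50% and 2% treated, the odds ratio of 1.75 could land anywhere from about 1.2 to about 2.1, depending on a treatment-DM association assumed to lie between 2.0 and 0.67. All these shares and associations are assumptions, and the shift is small if few cases have been treated. The direction cannot be known from the documents. The change should be made because it is nearly free and concerns the only confounder-adjusted (pre)DM analysis. The point does not reach the unadjusted result or the 261 per group, and for 10.2 the choice remains open.

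**What to change.** - In section 10.1, delete history of periodontal treatment from the adjustment set for periodontitis versus controls.
- In section 10.3, state that the item is collected and described but is not a covariate in that model, and define what counts as periodontal treatment and over what period.
- Keep the item in the baseline table by group, so that readers can see how many controls and cases were treated.
- Describe (pre)DM by treatment history within the periodontitis group only.
- In section 10.2, say that the adjusted severe versus mild/moderate result will be reported both with and without the covariate.

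The cost is a few lines of text and one extra model fit for 10.2. No new data are needed, no subjects are lost and the sample size does not change.

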### 4.4 Sample size calculation

The calculation of the sample size was based on a  $Chi^2$ -test having an  $\alpha$ <0.05 with 90% power and using the prevalence of diabetes of two groups (without periodontitis: 8.5%, severe periodontitis: 18.1%)(13). The required sample size is a minimum of 261 subjects per group.

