The missing data from included subjects will be imputed using the expectationmaximization method. Background variables, blood chemistry and demographic data between cases and controls will be analysed by Chi-analyses or t-tests where applicable. The primary and secondary outcome variables will be analysed both by univariate analysis and multivariate analysis (multiple logistic regression). The data will be analysed on an intention-to-treat basis (ITT).

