# APPENDIX 3: The 10-year-risk chart of ASCVD (for patients without known ASCVD) (30)

	Vrouwen									Mannen											
SBD		Niet	-rook	ster			Re	ookst	ter		Leef-	Niet-roker					Roker				
180	35	38	41	43	44	47	50	>50	>50	>50	tijd	>50	>50	>50	>50	>50	>50	>50	>50	>50	>50
160	28	31	33	35	36	38	41	44	46	48		45	48	>50	>50	>50	>50	>50	>50	>50	>50
140	22	24	26	28	29	31	33	36	38	39	70	37	40	42	44	46	49	>50	>50	>50	>50
120	18	19	21	22	23	25	27	29	30	32		30	32	34	36	38	40	43	45	48	50
180	14	17	20	24	30	27	32	37	45	>50		25	30	36	44	>50	45	>50	>50	>50	>50
160	10	12	14	17	21	19	22	27	32	39		18	21	26	32	40	33	39	47	>50	>50
140	7	8	10	12	15	14	16	19	23	28	65	12	15	18	23	29	23	28	34	42	>50
120	5	6	7	9	11	10	11	14	17	20		9	11	13	16	21	17	20	24	30	38
180	10	12	15	18	23	20	23	28	34	42		22	26	32	40	50	40	48	>50	>50	>50
160	7	8	11	13	16	14	17	20	24	30		15	19	23	29	36	29	35	42	>50	>50
140	5	6	7	9	12	10	12	14	17	21	60	11	13	16	20	26	20	25	30	38	47
120	4	4	5	7	8	7	8	10	12	15		8	9	12	15	19	14	18	22	27	34
180	5	6	8	10	12	10	12	15	18	22		13	16	20	26	32	25	31	38	47	>50
160	4	4	5	7	9	7	8	10	13	16		10	12	15	18	23	18	22	27	34	43
140	3	3	4	5	6	5	6	7	9	11	55	7	8	10	13	17	13	16	19	24	31
120	2	2	3	3	4	4	4	5	6	8		5	6	7	9	12	9	11	14	17	22
180	2	3	4	5	6	5	6	7	9	11		8	10	12	15	20	15	18	23	28	36
160	2	3	3	3	4	3	4	5	6	8		6	7	9	11	14	11	13	16	20	26
140	1	1	2	2	3	2	3	3	4	6	50	4	5	6	8	10	7	9	12	15	19
120	1	1	1	2	2	2	2	2	3	4		3	3	4	6	7	5	7	8	10	13
180	1	1	1	1	1	1	1	1	2	2		3	3	4	6	7	5	6	8	10	13
160	<1	<1	1	1	1	1	1	1	1	2		2	2	3	4	5	4	4	6	7	9
140	<1	<1	<1	1	1	<1	<1	1	1	1	40	1	2	2	3	4	3	3	4	5	7
120	<1	<1	<1	<1	<1	<1	<1	1	1	1		1	1	2	2	3	2	2	3	4	5
	4	5	6	7	8	4	5	6	7	8		4	5	6	7	8	4	5	6	7	8
			Rati	o tot	aal eł	olest	erol/	HDL						Rati	o tot	aal ch	olest	erol/	HDL		

Tabel 1. Risicotabel: 10-jaarsrisico op ziekte of sterfte door HVZ voor patiënten zonder HVZ

< 10% risico op ziekte of sterfte door HVZ; leefstijladviezen indien daar aanleiding voor is, zelden medicamenteuze behandeling.

10% tot 20% risico op ziekte of sterfte door HVZ; leefstijladviezen, medicamenteuze behandeling alleen bij risicoverhogende factoren en SBD > 140 mmHg en/of LDL > 2,5 mmol/l.

≥ 20% risico op ziekte of sterfte door HVZ; leefstijladviezen, medicamenteuze behandeling als SBD > 140 mmHg en/of LDL > 2,5 mmol/l.

Het risico bij patiënten met DM of RA kan worden geschat door bij de actuele leeftijd van de patiënt 15 jaar op te tellen.

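### Section 10.1 leaves the ASCVD-risk comparison unadjusted for age, the chart's largest input, and does not define a score for eligible subjects outside the chart's scope

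*Combined protocol and SAP*

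**What the plan says.** Sections 2 and 8.1.1 make the 10-year ASCVD risk a main outcome, read from the Appendix 3 chart. Section 10.1 describes the algorithm as one "which is adapted to the Dutch situation. No further adjustments will be done". The same section gives the (pre)DM outcome a second, exploratory analysis that adjusts for age among other characteristics.

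Two other places point the other way. Section 10 says that primary and secondary outcomes get both univariate and multivariate (multiple logistic) analysis. Section 10.3 lists age among the parameters used as covariates, without tying it to an outcome.

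On who is compared, Section 4.1 draws cases from referrals to the periodontal clinic and controls from check-up visitors. Section 8.3 adds: "The selection of subjects without periodontitis will be based on the following criteria: no interproximal alveolar bone loss on" recent bitewing radiographs, and no periodontitis by the Appendix 5 definition. Neither section mentions age. Section 4.2 admits anyone aged 18 or over, Section 4.3 lists no exclusions, and Section 10.1 puts every included subject in the analysis.

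The chart has age rows 40, 50, 55, 60, 65 and 70 and is for patients without known cardiovascular disease. For DM or RA, its footnote says the risk "kan worden geschat door bij de actuele leeftijd van de patiënt 15 jaar op te tellen", that is, by adding 15 years to the actual age. The only rule for missing values, in Section 10, is: "The missing data from included subjects will be imputed using the expectationmaximization method".

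**The concern.** There are two separate faults.

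The first is confounding by an input. Cases and controls come from different clinics, and controls are chosen for having no bone loss. If they differ in age, the chart turns that gap into a risk gap even when blood pressure, cholesterol and smoking are the same. The hypothesis in Section 1, that periodontitis patients have higher ASCVD risk, could then appear confirmed because controls are younger.

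The second is an undefined outcome. Some eligible subjects have no chart cell, yet all must be analysed. Extrapolating, dropping or imputing them can give different answers, and the plan does not choose. This gap does not cause the confounding and needs its own rule.

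**Working it through.** **The plan's own figure.** Section 4.4 plans "with 90% power and using the prevalence of diabetes of two groups", 8.5% and 18.1%. With mean rate 0.133, two-sided 5%:

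n = [1.960·√(2·0.133·0.867) + 1.282·√(0.085·0.915 + 0.181·0.819)]² / 0.096² = (0.941 + 0.609)² / 0.009216 ≈ 261.

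The stated 261 per group reproduces. It concerns diabetes only; the documents give no ASCVD-risk rate and no group ages.

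**How much of the chart is age.** All 480 cells of Appendix 3 were entered.

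| Age row | 40 | 50 | 55 | 60 | 65 | 70 |
|---|---|---|---|---|---|---|
| Cells ≥20%, of 80 | 0 | 6 | 17 | 38 | 47 | 78 |
| Non-smoking man, SBP 140, ratio 5 (%) | 2 | 5 | 8 | 13 | 15 | 40 |

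At age 55 the same man moves from 8% to 16% by smoking, from 6% to 16% as SBP goes from 120 to 180, and from 7% to 17% as the ratio goes from 4 to 8. A main-effects decomposition over the cells, equally weighted (below 1 set to 0.5, above 50 set to 50), gives age 60% of the variation, sex 10.5%, SBP 9%, smoking 6% and ratio 4%.

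**What an age gap alone does.** Assumed in both groups: age SD 12, SBP mean 132 (SD 17), ratio mean 4.5 (SD 1.1), 25% smokers, 50% men, 10% DM or RA, nearest age row. Only mean age differs. The groups are 261 controls and 522 with periodontitis. The probability of rejecting at two-sided 5% is

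Φ{[|p₁ − p₀| − 1.96·√(p̄(1 − p̄)(1/261 + 1/522))] / √(p₀(1 − p₀)/261 + p₁(1 − p₁)/522)}.

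For 45 versus 50: (0.053 − 1.96·0.0228)/0.0208 ≈ 0.40, so 66%.

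| Mean age, controls vs cases | Share at ≥20% risk | Chance of p<0.05 |
|---|---|---|
| 50 vs 50 | about 12% in both | nominal |
| 48 vs 50 | 9.6% vs 11.8% | 14% |
| 45 vs 50 | 6.5% vs 11.8% | 66% |
| 43 vs 50 | 5.0% vs 12.0% | 91% |
| 40 vs 50 | 3.2% vs 11.7% | 99% |

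With age SD 13, ratio SD 1.2 and no DM/RA shift, 45 versus 50 gives 5.4% versus 10.3%. If Bonferroni over four outcomes were applied (0.0125, critical value 2.498), the 66% becomes Φ[(0.053 − 2.498·0.0228)/0.0208] ≈ 43%.

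**When other risk factors differ too.** Assume smoking 20% versus 40% and DM/RA 8.5% versus 14%. At equal age the share at ≥20% is 10.9% versus 14.7%, a gap of 3.8 points. With a 5-year age gap it is 5.9% versus 14.8%, a gap of 8.9 points, so age adds 5.1 of 8.9, more than half. A 2-year age gap alone gives 8.6% versus 11.2%, or 2.6 points against the 3.8 from the other factors: less than half.

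**Who has no defined score.**
- Under 40, except subjects with DM or RA aged about 25–39, who shift to 40–54 and are inside the rows.
- Over 70.
- Over 55 with DM or RA, since 55 + 15 = 70 is the top row.
- Anyone with known ASCVD, who is eligible but outside the chart's scope.

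Under the first set of assumptions the age rows alone miss 26% at mean age 50, 35% at 45 and 48% at 40. With SD 13 and no shift, they miss 25% to 38% for mean ages 55 to 45. Known ASCVD would add to these.

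**Open-ended cells.** Forty cells are printed as above 50 and 14 as below 1: 54 of 480, or 11%. They have no exact value to average.

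**The case against.** The strongest reply is that the plan already covers age. Section 10 promises multivariate analysis of the primary outcomes, Section 10.3 names age as a covariate, and the first planned table would show any age gap. The sentence in 10.1 follows directly on how the risk is calculated and may mean only that the algorithm is not altered. This stands in part: the intention may be sound. But 10.1 is the outcome-specific text and it contrasts with the (pre)DM paragraph, so the passages need reconciling.

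Second, the stated aim is screening. For screening yield, crude absolute risk is a legitimate quantity, and the 15-year shift for DM or RA is how the chart defines risk. This stands. The crude result should be kept, and it would be wrong to say that it carries no information.

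A reader might infer that the group difference will mostly report age. The documents do not support that without group ages: it depends on a gap of several years, and at equal ages the bias vanishes. A reader might also infer that unscored subjects will be imputed by EM, or that ANOVA will average the chart risk. Neither is stated. No section says that out-of-chart subjects count as missing, and 10.1 names ANOVA and Chi² jointly for outcomes it calls categorical. Finally, 10.1 refers to an ESC-derived algorithm that is not reproduced, so its age range cannot be checked.

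**Conclusion.** The concern holds in conditional form. Section 10.1 plans no adjustment of the ASCVD-risk comparison for the chart's largest input, no age matching is planned, and the text conflicts with Sections 10 and 10.3. A 5-year age gap alone could roughly double the share at or above 20% risk (about 5–7% versus 10–12%) and give p<0.05 in about two studies out of three at the unadjusted level. Those sizes rest on assumed age, blood pressure, cholesterol, smoking and DM/RA distributions; only the chart counts come from the documents.

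Separately, the score is undefined for subjects outside the age rows or with known ASCVD. The share is an estimate (25–48% for the age rows), but the absence of a rule is a fact of the plan. Because the end rows almost fix the band (2 of 80 cells reach 10% at age 40; 78 of 80 reach 20% at age 70), a short rule resolves most of the age part.

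**What to change.** In Section 10.1, reconciled with Sections 10 and 10.3:

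1. Keep the crude chart risk as the screening-yield result. Compare its three printed bands (below 10%, 10–20%, 20% or more) by Chi², and do not average the open-ended cells.
2. Beside it, add a comparison adjusted for age and sex, for example logistic regression at the ≥10% and ≥20% cuts. Let age enter flexibly, since the chart is far from linear in age (15% to 40% between rows 65 and 70 in the example above).
3. Add an age-adjusted comparison of SBP, total/HDL cholesterol ratio and smoking. These do not carry the 15-year DM/RA shift.
4. Score ages, or shifted ages, outside the rows at the nearest end row and do not impute them. Report subjects with known ASCVD separately.
5. Add a sensitivity analysis limited to subjects inside the chart's scope.

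Reading everyone at one common age row is an alternative to step 2, but it leaves any rise of SBP with age in place. With an assumed 0.5 mmHg per year, reading all at row 60 still gives 9.6% versus 10.8% at ≥20% for mean ages 45 and 50. Ordinary age adjustment is simpler.

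The cost is wording and one extra table; Sections 8.1.3 and 8.3 already collect every input. The adjusted result is not an absolute risk, so it stands beside the crude one. End-row scoring slightly overstates risk under 40 and understates it over 70. Section 10.2 repeats the primary procedures, so the change carries over to the comparison of severity groups.
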